10.2.2. Radiologic Response

Radiologic response will be evaluated by RECIST 1.1 and immune-related RECIST criteria. Radiologic responses will be correlated with pathologic responses and clinical outcomes, including RFS. Radiologic responses to combined chemoradiation prior to surgery are seen in approximately 60-65% of patients. We anticipate that neoadjuvant immunoradiation will yield similar response rates, although this is unknown.

10.2.3. Immune-related RECIST

The response to immunotherapy may differ from the typical responses observed with cytotoxic chemotherapy including the following^{17, 92}:

- Response to immunotherapy may be delayed
- Response to immunotherapy may occur after PD by conventional criteria
- The appearance of new lesions may not represent PD with immunotherapy
- SD while on immunotherapy may be durable and represent clinical benefit.

Based on the above-described unique response to immunotherapy and based on guidelines from regulatory agencies, e.g., European Medicines Agency's "Guideline on the evaluation of anti-cancer

18-Nov-2020 Page **112** of **164**

IND #134339

medicinal products in man" (EMA/CHMP/205/95/Rev.4) for immune modulating anti-cancer compounds, the study may wish to implement the following in addition to standard RECIST 1.1 criteria:

- RECIST will be modified so that PD must be confirmed at the next scheduled visit, preferably, and no earlier than 4 weeks after the initial assessment of PD in the absence of clinically significant deterioration.
- Therefore, in patients with PD by RECIST 1.1 on CT scan prior to surgery, a second CT can be performed 4 weeks later to confirm PD.

Modification of RECIST as described may provide a more complete evaluation of its anti-tumor activity than would be seen with conventional response criteria. Nonetheless, the efficacy analysis will be conducted by programmatically deriving each efficacy endpoint based on RECIST 1.1 criteria.

Of note, clinically significant deterioration is considered to be a rapid tumor progression that necessitates treatment with anti-cancer therapy other than durvalumab +/- tremelimumab or with symptomatic progression that requires urgent medical intervention (e.g., central nervous system metastasis, respiratory failure due to tumor compression, spinal cord compression).

10.2.4. Recurrence-free Survival

Recurrence-free survival (RFS) will be defined as the time from commencement of therapy until the development of local or distant recurrent disease. The development of local or distant recurrent disease will be detected radiologically by CT scan performed as per the Schedule of Assessments (Figure 1), by RECIST 1.1 criteria. RFS will be correlated with pathologic response and radiologic response to study therapy. Progression-free survival for patient treated with neoadjuvant chemoradiation prior to surgery in patients with stage III NSCLC was a median of 12.8 months as reported by Albain and colleagues. We anticipate to see similar or potentially improved results in this study. Subject deaths without recurrence will be censored.

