2.2. Secondary Objective(s)

- (1) Examine pathologic responses in post-treatment resection specimens, in patients with resectable stage III NSCLC treated with preoperative immunoradiation followed by surgery.
- (2) Examine radiologic responses in stage III resectable NSCLC treated with preoperative immunoradiation, using RECIST 1.1 and immune-related (ir) RECIST criteria
- (3) Evaluate recurrence-free survival (RFS) in patients with stage III resectable NSCLC treated with preoperative immunoradiation followed by surgery, where RFS is defined as the time from commencement of therapy until the development of local or distant recurrent disease.
- (4) Evaluate surgical morbidity and mortality in patients with stage III resectable NSCLC treated with preoperative immunoradiation followed by surgery, where morbidity is defined as the number treatment-related AEs, and mortality is the number of deaths, from the day of surgery until 30 days postoperatively or 100 days after the last dose of immunotherapy, whichever is longer.
- (5) Evaluate overall survival (OS) in patients with stage III resectable NSCLC treated with preoperative immunoradiation followed by surgery, where OS is defined as the time from commencement of therapy until death from any cause.

18 Nov 2020 Page **54** of **164**

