6.2.2.3. Prescription Dose and Fractionation

• Patients will receive treatment 5 days per week in once daily fractionation, 1.8-2.0 Gy per fraction. The total dose will be 45Gy in 25 fractions.

18 Nov 2020 Page **74** of **164**

^{*} Weight-based dosing should be utilized for patients < 30 kg equivalent to 20 mg/kg durvalumab Q4W and 1 mg/kg tremelimumab Q4W

A plan for potential definitive radiation therapy prior to therapy administration (i.e. to 60-70Gy) will be generated concurrently with the
neoadjuvant treatment plan to 45 Gy to ensure that patients who may no longer be found to be surgical candidates, may be offered a
potentially curative course of treatment without significant delay.

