12.3.2. Analysis Plan for Secondary Endpoints

Pathologic response will be stratified as showing MPR (>90% reduction in tumor cells), PR (10-90%) or NR (0-10%). The proportion of patient's whose tumor samples achieve MPR, PR and NR will be tabulated. The relationship between pathologic response in post-treatment resection specimens and clinical outcomes such as RFS, OS and surgical morbidity/mortality will be assessed through log-rank test and Cox proportional hazards (PH) model. Radiologic response will be evaluated by RECIST 1.1 and immunerelated RECIST criteria at time points specified in the Schedule of Assessments (Figure 1). The relationship between radiologic response in post immunoradiation CT scans and clinical outcomes including RFS, OS and surgical morbidity/mortality will be assessed using log-rank and Cox PH model. RFS will be defined as time from commencement of study therapy until the date of radiologic evidence of local or distant recurrent NSCLC. OS) will be defined as the time from commencement of protocol treatment until death due to any cause. RFS and OS will be calculated using the Kaplan-Meier method, and will be analyzed as time-to-event data. All adverse events that occur from the time of surgery until 30 days post-surgery or from the last dose of immunotherapy until 100 days, will be similarly summarized by type and grade. Any deaths that occur in this time period will be recorded. Attributions to the development of AEs or death in this time period will be recorded as either definitely related, possibly related, probably related or unrelated to study therapy.

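### RFS runs from the first dose but counts only recurrence; progression before surgery and non-resection have no rule, and the literal reading gives a too-favourable curve

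*Combined protocol and SAP*

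**What the plan says.** Sections 2.2, 10.2.4 and 12.3.2 start RFS at commencement of therapy and give it one kind of event. Section 10.2.4 reads: "Recurrence-free survival (RFS) will be defined as the time from commencement of therapy until the development of local or distant recurrent disease". Section 12.3.2 reads: "RFS will be defined as time from commencement of study therapy until the date of radiologic evidence of local or distant recurrent NSCLC". The synopsis has the same event but starts the clock at study enrollment. The only explicit censoring rule for RFS is in 10.2.4: "Subject deaths without recurrence will be censored".

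The objective in 2.2 is worded for operated patients: "Evaluate recurrence-free survival (RFS) in patients with stage III resectable NSCLC treated with preoperative immunoradiation followed by surgery". No RFS analysis set is defined.

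The plan foresees patients who fail before or instead of surgery:
- Section 10.2.3: "in patients with PD by RECIST 1.1 on CT scan prior to surgery, a second CT can be performed 4 weeks later to confirm PD".
- Section 6.2.2.3 prepares a definitive radiation plan for "patients who may no longer be found to be surgical candidates".
- A note to Figure 1 gives a safety visit for patients who do not go to surgery.
- Section 6.2.3.1 replaces patients who turn out to need a pneumonectomy and keeps following them for safety.

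None of these places says what happens to such patients in the RFS analysis. Section 10.2.4 then sets RFS beside a median progression-free survival of 12.8 months from a chemoradiation trial and expects similar or better results.

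**The concern.** Recurrence presupposes that disease was removed. Figure 1 places the pre-surgery visits at weeks 11-15, so for roughly the first three months nothing can recur in the ordinary sense. A patient whose tumour grows in that period has had the failure that an endpoint timed from the first dose should capture, yet the definition has no place for it.

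Three uses of RFS are exposed:
- **The benchmark.** An endpoint that omits progression before surgery is compared with a progression-free figure.
- **The association analyses.** Section 12.3.2 relates radiologic response to RFS by log-rank test and Cox model. A patient with progression on the pre-surgical scan could be the worst radiologic responder and have no RFS event.
- **The feasibility review.** If that boundary is reached, 12.2.3 weighs RFS among the benefits. That is when patients are not reaching surgery as planned, so the bias may be largest when RFS is used.

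Follow-up may not repair the gap. The long-term follow-up table leaves scans after confirmed progression to local practice, so a later study scan recording recurrence is not assured.

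**Working it through.** The plan states no event target, power or expected rate for RFS, so there is no planned figure to reproduce. The check asks which way, and roughly how far, the estimate moves.

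**Inputs.** From the plan: the 12.8-month median (10.2.4), 16 evaluable patients per cohort (12.1) and surgery at about weeks 11-15 (Figure 1). Assumed: an exponential event-free curve with that median, and a share u of patients failing before surgery, varied from 10% to 25%.

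**Formulas.**
- Failures counted: S(t) = 2^(-t/12.8), so S(12) = 2^(-0.9375) = 52.2%.
- Failures censored when they occur: after surgery the Kaplan-Meier curve is S(t)/(1 - u).
- Failures left out of the analysis set: the same later curve, S(t)/(1 - u).
- Failures kept as recurrence-free throughout: u + S(t).

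**Results at 12 months, with the median in months in brackets.**

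| u | of 16 patients | counted | censored or left out | kept recurrence-free |
|---|---|---|---|---|
| 10% | 1.6 | 52.2% (12.8) | 58.0% (14.7) | 62.2% (16.9) |
| 15% | 2.4 | 52.2% (12.8) | 61.4% (15.8) | 67.2% (19.4) |
| 25% | 4.0 | 52.2% (12.8) | 69.6% (18.1) | 77.2% (25.6) |

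Example for u = 10%: 52.2/0.90 = 58.0, and 10 + 52.2 = 62.2. The shift runs from 58.0 - 52.2, about 6 points, to 77.2 - 52.2 = 25 points. The last column is an upper end, because some of these patients could later have a scan that is recorded as recurrence.

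**Is the range of u plausible?** Under the same assumed curve, the share failing by week 11 (2.53 months) is 1 - 2^(-2.53/12.8) = 12.8%, and by week 15 (3.45 months) it is 17.0%. That is about 2 to 3 of 16 patients.

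**Small-sample check.** In 20,000 simulated cohorts of 16 with surgery at week 13 (about 15% failing earlier), the mean 12-month estimate was 52.1% with failures counted, 61.3% censored and 67.0% kept. The bias is about +9 to +15 points.

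Deaths without recurrence, which 10.2.4 censors, are not modelled separately here.

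**The case against.** The best counter-argument is that the plan already captures progression. Section 10.2.4 detects events on the Figure 1 scans by RECIST 1.1. In the main part of Figure 1, the only post-baseline CT with a RECIST read is the pre-surgical one. Section 10.2.3 says that efficacy endpoints will be derived from RECIST 1.1, and the benchmark is a progression-free median. An analyst could reasonably count progression before surgery. This part stands: the documents leave that reading open. But 10.2.4 uses RECIST to detect recurrent disease and nowhere equates progression with recurrence. An unresected patient without progression still has no rule.

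Stronger readings are tempting and are not supported:
- A reader might infer that the plan orders living patients with pre-surgical failure to be censored. It does not. The written rule covers deaths only; for the living the plan is silent, and the wording of 2.2 also allows exclusion.
- A reader might take the 75% feasibility threshold as tolerating 4 of 16 unresected patients. That rule concerns treatment-related delay, and Table 10.5 stops at 6 of 15-16. It is no evidence for the share failing because of disease.
- A reader might count every unresected patient as a failure. Section 6.2.2.3 does not say that candidacy is lost because of disease, and it provides a potentially curative alternative.

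Precision also limits the point. The exact 95% interval for 8 of 16 is roughly 25-75%, so a shift from a single patient is small beside sampling error. The planned correlation of pathologic response with RFS uses resected patients only, so never-resected patients do not enter it.

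**Conclusion.** The gap is real. RFS is timed from the first dose with recurrence as its only defined event, and the plan leaves open what happens to living patients who progress before surgery or are never resected. Censoring them, keeping them as recurrence-free and leaving them out all push the curve upward and break comparability with the 12.8-month benchmark. Only a reading that the plan does not state avoids this for progression.

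The size rests wholly on the exponential shape and the assumed 10-25% failing before surgery: 52% at 12 months with failures counted, against 58-70% or 62-77%. The direction does not depend on those assumptions, provided that at least one patient fails before surgery.

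RFS is a descriptive secondary endpoint. The safety and feasibility results are unaffected. What suffers is the RFS estimate, its comparison with the benchmark and its association with radiologic response.

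**What to change.** In 2.2, 10.2.4, 12.3.2 and the synopsis, define event-free survival in all treated patients from the first dose, with these events:

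1. RECIST 1.1 progression before surgery, dated at the first scan showing it. State whether confirmation is required, consistently with 10.2.3, where it is optional.
2. Disease progression that precludes resection.
3. Recurrence after resection.
4. Death without recurrence, if the name event-free survival or the comparison with progression-free survival is used. Reconcile this with the sentence in 10.2.4 that censors such deaths.

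State the handling and the censoring date for patients not resected for other reasons; they stay at risk for later progression. Report RFS from surgery in resected patients as a supplement. Reconcile the synopsis start date (enrollment) with commencement of therapy.

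The cost is protocol and SAP wording. The downside is a somewhat less favourable curve.

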- 2. Feasibility: To evaluate whether durvalumab (cohort 1) or durvalumab plus tremelimumab (cohort 2) delivered concurrent with thoracic radiation (RT) and in the pre-surgical window prior to surgical resection, will not delay the time to surgery beyond the planned date of surgical resection, in patients with stage III resectable NSCLC.

Secondary Objective(s):

1. Pathologic Response

To determine whether durvalumab (cohort 1) or durvalumab plus tremelimumab (cohort 2) delivered concurrent with thoracic radiation (RT) and in the pre-surgical window prior to surgical resection, will induce a pathologic response in patient's primary tumors and draining lymph nodes, in patients with stage III resectable NSCLC.

2. Radiologic Response

To determine whether durvalumab (cohort 1) or durvalumab plus tremelimumab (cohort 2) delivered concurrent with thoracic radiation (RT) and in the pre-surgical window prior to surgical resection, will induce a radiologic response in in patient's primary tumors and draining lymph nodes, in patients with stage III resectable NSCLC.

3. Recurrence-Free Survival (RFS)

To determine whether durvalumab (cohort 1) or durvalumab plus tremelimumab (cohort 2) delivered concurrent with thoracic radiation (RT) and in the pre-surgical window prior to surgical resection, will delay the development of local or distant recurrent non-small cell lung cancer, in patients with stage III resectable NSCLC.

4. Surgical morbidity and mortality

To determine whether durvalumab (cohort 1) or durvalumab plus tremelimumab (cohort 2) delivered concurrent with thoracic radiation (RT) and in the pre-surgical window prior to surgical resection, will lead to unacceptable rates of postoperative morbidity or mortality when compared to historical controls, in patients with stage III resectable NSCLC.

5. Overall Survival

To determine whether durvalumab (cohort 1) or durvalumab plus tremelimumab (cohort 2) delivered concurrent with thoracic radiation (RT) and alone in the pre-surgical window prior to surgical resection, will result in an overall survival improvement in comparison to historical controls, in patients with stage III resectable NSCLC.

Exploratory Objective(s):

1. Genomic and neoantigen correlates.

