Subjects in this study will be males or females 18 years of age or older. Subjects must have histologically confirmed stage III NSCLC deemed surgically resectable by a thoracic surgeon with lobectomy, have adequate organ and marrow function, no prior history of active autoimmune disease or active infections, and have an ECOG performance status of 0-1. Patients with a prior history of chest radiation, interstitial lung disease/pneumonitis, or who would require a pneumonectomy, will be excluded.

Study Assessments and Criteria for evaluation:

Safety Assessments:

1. Safety:

All adverse events (including serious and non-serious, as well as adverse events of special importance AESIs) will be recorded from commencement of therapy until 30 days after surgical resection or 100 days after the last dose of immunotherapy, whichever is longer. Adverse events will be collected and recorded according to CTCAE version 4.03

2. Feasibility:

The number of dose-limiting toxicities that delay the time of planned surgery beyond the planned surgical window (>8 weeks) after completion of thoracic RT. DLTs will be collected and recorded according to CTCAE version 4.03

3. Surgical Morbidity and Mortality:

All adverse events (including serious and non-serious, as well as adverse events of special importance AESIs) or deaths that occur from the time of surgery until 30 days post-surgery or 100 days after the last dose of immunotherapy, whichever is longer.

Efficacy Assessments:

1. Pathologic Response Rate:

Pathologic response evaluated by two thoracic pathologists as described by Pataer et al (J Thorac Oncol 2012), and stratified into major pathologic response (MPR), partial response (PR) and no response (NR).

2. Radiologic Response:

Radiologic response by RECIST 1.1 and immune-related RECIST criteria.

3. Recurrence-Free Survival:

The time from study enrollment until radiologic evidence of local or distant recurrent NSCLC.

4. Overall Survival

The time from study enrollment until death from any cause.

Statistical methods:

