10.2.5. Overall Survival

OS will be defined as the time from commencement of therapy until death from any cause. Patients will be followed with a telephone call or clinic visit every 3 months for years 1-3 for survival status. The cause of death will be documented if known and relationship to study drug as per section 9.3.2. OS for patient treated with neoadjuvant chemoradiation prior to surgery in patients with stage III NSCLC was a median of 23.6 months as reported by Albain and colleagues. We anticipate to see similar or potentially improved results in this study.

18-Nov-2020 Page **113** of **164**

IND #134339

11. Study Drug Information

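### RFS counts recurrence only and censors deaths, so the planned Kaplan-Meier curve is time to recurrence and exceeds a death-inclusive RFS once a patient dies without recurrence

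*Combined protocol and SAP*

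**What the plan says.** RFS is defined in four places, and each makes recurrence the only event:

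- Synopsis, Efficacy Assessments: "The time from study enrollment until radiologic evidence of local or distant recurrent NSCLC".
- Section 2.2, third objective: "where RFS is defined as the time from commencement of therapy until the development of local or distant recurrent disease".
- Section 10.2.4: from start of therapy to local or distant recurrence, with the added rule "Subject deaths without recurrence will be censored".
- Section 12.3.2: "RFS will be defined as time from commencement of study therapy until the date of radiologic evidence of local or distant recurrent NSCLC".

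Section 12.3.2 names the estimator, "RFS and OS will be calculated using the Kaplan-Meier method", and plans log-rank tests and Cox models relating pathologic and radiologic response to RFS. No section counts death as an RFS event, names a competing-risk method, or plans a sensitivity analysis that includes deaths.

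Two other statements bear on how the endpoint is read. The RFS objective in the Synopsis asks whether treatment "will delay the development of local or distant recurrent non-small cell lung cancer". Section 10.2.4 cites a progression-free survival after neoadjuvant chemoradiation that "was a median of 12.8 months", and expects a similar or better result here.

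Section 10.2.5 makes death from any cause the OS event and provides for collecting it: "Patients will be followed with a telephone call or clinic visit every 3 months for years 1-3 for survival status".

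**The concern.** A reader takes recurrence-free survival to be the probability of being alive without recurrence. Under this plan, a patient who dies around surgery without recurrence leaves the risk set as if merely lost to follow-up, and the curve does not drop. In a cohort of 16 in which one patient dies before any recurrence or censoring, a death-inclusive curve falls to 15/16 = 93.75% while the planned curve stays at 100%. With two such deaths the comparison is 14/16 = 87.5% against 100%.

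The matter has some practical weight. Section 12.2.3 says that if the feasibility boundary is reached, prolonged RFS is one of the benefits to be weighed against the risks. An RFS that cannot register a death without recurrence is a weak measure for that purpose.

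**Working it through.** The documents give no event count, power or sample size for RFS, so there is no design figure to reproduce. The check has two parts: direction, which is exact, and size, which needs assumptions.

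**Direction.** A patient who dies leaves the risk set at death under either definition, so the number at risk, n, is the same at every event time. With r recurrences and d deaths without recurrence at that time, the Kaplan-Meier factors are

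- deaths censored (the plan): 1 − r/n
- deaths counted: 1 − (r + d)/n

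The first is never smaller, and the two are equal while d = 0. As a check, 5,000 cohorts of 16 were simulated with exponential recurrence and death, a 36-month cut-off, and 15% of first events being deaths. The planned curve was never below the death-inclusive one. It was strictly above it at some time in all 4,456 cohorts with at least one death without recurrence.

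**Size: inputs.**

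- Recurrence: exponential with a 12.8-month median. The figure is the one in section 10.2.4; its use as a recurrence median is an assumption.
- Deaths: a fraction q of patients still recurrence-free dies at month 3, about the planned time of surgery (assumption).
- q = 0.5%: section 1.6.5, one death after lobectomy as a share of the whole cited series. It is not a lobectomy-specific rate.
- q = 4%: the perioperative norm in section 3.1.6.2.
- Exactly 1 or 2 of 16 patients: illustrative.

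**Formulas.** λ = ln 2/12.8 = 0.05415, so S(3) = exp(−3λ) = 0.850 and S(12) = exp(−12λ) = 0.522. For t > 3, RFS counting deaths is (1 − q)·exp(−λt), with median ln[(1 − q)/0.5]/λ. For k of 16 patients, q = (k/16)/S(3): 0.0625/0.850 = 0.0735 for k = 1, and 0.125/0.850 = 0.147 for k = 2.

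| Deaths without recurrence | Median, plan | Median, deaths counted | 12-month, plan | 12-month, deaths counted | Gap (points) |
|---|---|---|---|---|---|
| q = 0.5% | 12.8 | 12.7 | 52.2% | 52.0% | 0.2 |
| q = 4% | 12.8 | 12.0 | 52.2% | 50.1% | 2.1 |
| 1 of 16 | 12.8 | 11.4 | 52.2% | 48.4% | 3.8 |
| 2 of 16 | 12.8 | 9.9 | 52.2% | 44.5% | 7.7 |

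**Sampling error.** The 95% half-width at n = 16 is 1.96·√(0.522 × 0.478/16) = 0.245, about 24 points.

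**How likely is a gap?** The chance of at least one perioperative death among 16 is 1 − 0.96^16 = 48% at a 4% rate and 1 − 0.995^16 = 7.7% at 0.5%.

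**Sensitivity to calibration.** If 12.8 months is instead taken as the death-inclusive median, and a share f of first events are deaths occurring at a constant rate, the planned median is 12.8/(1 − f). For f = 5% to 30% (not given in the documents) this is 13.5 to 18.3 months, with 12-month gaps of 1.7 to 11.2 points. The direction is the same, and the gap is still inside the sampling error.

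**Time-to-recurrence reading.** Cumulative incidence of recurrence at 12 months is [1 − S(3)] + (1 − q)[S(3) − S(12)]: 45.4% with 1 of 16 deaths and 43.0% with 2 of 16. One minus the planned curve gives 47.8%.

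**The case against.** The strongest reply is that the choice is deliberate and consistent. Four definitions agree on the event, the censoring rule is explicit, and it fits an objective about delaying recurrence. Kaplan-Meier with deaths censored estimates a definable quantity: the recurrence-free probability with death removed, if censoring is independent. That stands, and it confines the fault to the mismatch between label and content.

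Nor are the deaths hidden. They count in OS, perioperative deaths are a separate secondary endpoint (sections 2.2, 10.1.3 and 12.3.2), and treatment-related grade 5 events have a stopping rule (Table 10.3). The upper scenario is also partly limited by the protocol: section 3.1.6.2 closes the study if a related early death takes mortality above the historical norm. Two deaths in a completed cohort nevertheless remain possible. Table 10.3 requires three once 11 to 16 patients are evaluable, and deaths judged unrelated fall outside both rules.

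Three stronger readings are tempting, and the documents do not support them:

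- **The RFS curve will be too high.** It is higher only after a death without recurrence; without one, the two curves are identical.
- **Neither reading of the endpoint is estimated correctly.** The overstatement of recurrence arises only if one minus the curve is reported as recurrence risk, and no section plans that.
- **The comparison with 12.8 months is biased in this trial's favour.** That requires the cited PFS to count deaths, which the documents do not say. Section 10.2.4 uses the figure for an expectation, not a test, and the Synopsis sets OS and surgical outcomes, but not RFS, against historical controls.

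**Conclusion.** The point holds as a mismatch between the endpoint's name and what will be estimated. The direction is certain once a death without recurrence occurs. The size rests on assumptions about recurrence and the timing of deaths: it is negligible to small at the mortality figures the protocol quotes, and reaches about 8 points only in the two-death scenario. A result within sampling error is still worth correcting, because the shift is systematic and its direction is known.

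The reach is limited. RFS is secondary, and the safety and feasibility analyses and their stopping rules do not use this definition. The log-rank and Cox analyses in section 12.3.2 remain valid as cause-specific associations with recurrence, though they should be described that way. This should be corrected before analysis, but it does not threaten the trial's main conclusions.

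**What to change.** Either of two changes resolves it.

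1. **Keep the name.** In the Synopsis and sections 2.2, 10.2.4 and 12.3.2, define the RFS event as the first of recurrence or death from any cause. Delete the censoring sentence in section 10.2.4. Censor living, recurrence-free patients at their last disease assessment. Add death to the RFS objective in the Synopsis so that it matches.
2. **Keep the content.** Rename the endpoint time to recurrence, report cumulative incidence with death as a competing event, and note that the 12.8-month PFS figure may not be like for like.

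The cost is wording; deaths are already collected for OS. Under the first option the reported RFS will be slightly shorter if such deaths occur (12.0 against 12.8 months at 4% under the assumptions above).

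I would not add a rule closing RFS when scheduled first-year imaging ends (section 8.1.4). It could discard recurrences found during the follow-up in years 2 and 3 that the long-term follow-up table allows per standard of care. Separately, the start date needs reconciling: the Synopsis counts from enrollment, the other three definitions from start of therapy.
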